8.3.3 Protections of Human Subjects

Protections for human subjects of research are required under Department of Health and Human Services (HHS) regulations at 45 CFR 46. Subpart A of the HHS regulations constitutes the Federal Policy (Common Rule) for the Protection of Human Subjects, which has been adopted by an additional 16 Executive Branch Departments and Agencies.

Each institution engaged in (non-exempt) HHS-supported human subjects research must provide a written Assurance of Compliance, satisfactory to the Office for Protection from Research Risks (OPRR), that it will comply with the HHS human subjects regulations. -- 45 CFR 46.103(a)

8.3.4 Summary of the Risks and Benefits

This study will evaluate dosing strategies and route of administration for a commonly used, FDA approved medication for AHF (furosemide). Both the dosing range being evaluated (1 vs. 2.5 x oral dose) and the route of administration (IV intermittent bolus vs. continuous infusion) are both well within current standard of care. As such, it is not anticipated that participation in this study will be associated with increased risks beyond that of standard AHF therapy. The risk of loss of confidentiality will be managed using polices and procedures designed to protect confidentiality described above. There will be no specific benefits anticipated beyond contributing to better understanding of optimal care of AHF that may benefit the study subject during future AHF episodes.

9. BASELINE EVALUATIONS AND RANDOMIZATION

A complete schedule of assessments throughout the study is given in Appendix A.

9.1 Randomization

After providing informed consent and signing the ICF, all study subjects will be randomized using procedures determined by the DCC to one of 4 treatment groups, based on the 2 x 2 factorial design defined above. Randomization will be 1:1:1:1. Blocking will be used to ensure relatively equal distribution of patients to each arm. Randomization will be stratified by clinical site.

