9.2 Baseline Assessments

At the time of randomization, all study subjects will undergo

- Directed history and physical examination, focused on signs and symptoms of congestion
- Vital signs (including O₂ saturation and weight)
- Concomitant cardiovascular medications
- Creatinine, BUN, and electrolytes (local laboratory)
- Patient Global Well being assessment (PGA) by VAS (see Appendix C)
- Dyspnea assessment by VAS (see Appendix C)
- Blood sample for biomarkers core laboratory

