14.2 Analysis of Primary Endpoints

The primary analysis will be made on an intention-to-treat basis, with patients allocated to the treatment to which randomized. General linear models will be used to examine the effect of each of the main effects on the two co-primary outcomes. The dependent variables in the regression model will be the change in creatinine value from baseline to 72 hours and the AUC for the PGA VAS from baseline through 72 hours. Independent variables in the model will include the main effects of furosemide dose and mode of administration, and the baseline creatinine level. An interaction term will be included if the p-value for that parameter estimate is less than 0.025. For each co-primary outcome, the two main effects will be that the treatment (either dose or mode of administration) has no effect on either of the co-primary outcomes.

We anticipate that some patients may die before all scheduled post-baseline creatinine values can be taken, and that these losses will introduce bias into the main effects comparisons. For the primary analyses, the values imputed will be 0 for the PGA VAS after the time of death and the highest post-baseline creatinine measurement. Sensitivity analyses, including analysis of only complete cases and imputing the worst creatinine value for deaths, will be employed to assess the degree to which these missing values impact the results.

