14.3 Sample Size

For purposes of power calculations, we have applied a Bonferroni adjustment to the alpha level (0.05/2 = 0.025) to allow for two co-primary endpoints. We assume that the effect of both dose and administration mode will be additive (i.e. no interaction). In our sample size calculations shown below we assess the sensitivity of the power to subadditivity of the main effects. Due to the short-term nature of the study, missing data due to loss-to-followup are expected to be rare. In addition, because this study design is testing initial treatment strategies, we do not anticipate problems with adherence to the protocol guidelines.

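### Randomization is stratified by clinical site but the primary model omits site; if site is related to outcome, the 2.5% tests are somewhat conservative and a little precision is forgone

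*Protocol*

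**What the plan says.** On allocation, protocol section 9.1 states "Randomization will be 1:1:1:1", then "Blocking will be used to ensure relatively equal distribution of patients to each arm", then "Randomization will be stratified by clinical site". The block size is not given. Section 8.2 places recruitment at 9 regional centers plus an unstated number of satellites.

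On analysis, section 14.2 states "General linear models will be used to examine the effect of each of the main effects on the two co-primary outcomes" and then "Independent variables in the model will include the main effects of furosemide dose and mode of administration, and the baseline creatinine level". The only further term mentioned is conditional: "An interaction term will be included if the p-value for that parameter estimate is less than 0.025". Site does not appear in this list, and no other section says that the analysis accounts for it.

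The significance level comes from section 14.3, where "we have applied a Bonferroni adjustment to the alpha level (0.05/2 = 0.025) to allow for two co-primary endpoints". The captions of Figures 5 and 6 make it two-sided.

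**The concern.** Blocking within site balances the arms on site. Differences in outcome between sites then largely drop out of the true sampling error of a treatment comparison. A model without site does not know this and leaves the between-site variation in its residual. The estimate is unbiased, but the model's standard error describes a less precise design than the one that was run.

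If sites do differ, confidence intervals are wider than they need to be and each test rejects less often than 2.5% under the null. One co-primary endpoint is a safety measure, change in creatinine. There a conservative test makes a real difference harder to show.

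Site differences are plausible, though not documented. The PGA is a subjective scale collected at many hospitals. Early switch to oral diuretics and discharge are left to clinicians, and under section 5 early discharge triggers carry-forward in both primary endpoints.

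**Working it through.** **Inputs.** 300 patients, so 150 v. 150 for each main effect (section 5). Two-sided alpha 0.025 (section 14.3 and Figure 5 caption). Creatinine difference 0.20 mg/dL with SD 0.5 (section 14.3.1). PGA AUC difference 600 points with SD 1500 (section 14.3.2). Both are 0.4 SD, so one calculation serves both endpoints. The share of outcome variance due to site, called ρ here, is not in the protocol and is an assumption.

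**The plan's own figure.** The critical value is z = 2.241. The standardized effect is m = 0.2 / (0.5 × √(2/150)) = 3.464. Power is Φ(3.464 − 2.241) = Φ(1.223) = 88.9%, against the stated 88%. With SD 0.4 the result is 98.2%, against the stated 98%. Both reproduce.

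**Effect of leaving site out.** With balance within site, the true variance of the treatment difference is (1 − ρ) times the variance that the model reports. Hence:

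- reported SE / true SE = 1/√(1 − ρ)
- actual alpha = 2 × [1 − Φ(2.241/√(1 − ρ))]
- power without site = Φ((3.464 − 2.241)/√(1 − ρ))
- power with site = Φ(3.464/√(1 − ρ) − 2.241)

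Both power formulas use the normal approximation, so the two columns are on the same basis.

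| Assumed ρ | SE ratio | Actual alpha, site omitted | Power, site omitted | Power, site included | Forgone (points) |
|---|---|---|---|---|---|
| 0 | 1.000 | 2.50% | 88.93% | 88.93% | 0 |
| 1% | 1.005 | 2.43% | 89.04% | 89.25% | 0.2 |
| 5% | 1.026 | 2.15% | 89.52% | 90.54% | 1.0 |
| 10% | 1.054 | 1.81% | 90.13% | 92.07% | 1.9 |

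Pushed to ρ = 20%, actual alpha is 1.22% and power is 91.42% without site against 94.86% with it.

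**Check by simulation.** Assumed: 300 patients, 9 or 30 sites of unequal size, permuted blocks of 4, a baseline covariate unrelated to outcome, 4,000 runs per setting.

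- At ρ = 10% without site, the mean model SE was 0.0574 (9 sites) and 0.0578 (30 sites), against empirical SEs of 0.0546 and 0.0550. The ratios are both about 1.05, as the formula gives. Null rejection was 1.85% and 1.58%.
- With site as fixed effects, null rejection lay between 2.1% and 2.6% in all settings. The simulation standard error is √(0.025 × 0.975/4000) = 0.25 points, so this agrees with 2.5%.
- At ρ = 0, adding site changed simulated power from 88.8% to 88.9% with 9 sites and from 89.2% to 88.6% with 30 separate fixed effects. This is the price of adjusting when site does not matter.

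**The case against.** The strongest counter-argument is that the consequence is conditional and small. That stands. With no site effect there is no loss, and at 1% the change in alpha is negligible. A reader might infer from the mismatch that the standard errors are in fact too large. The protocol cannot support that, because it gives no information on variation between sites.

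A reader might also infer that the power bought by stratifying is lost, or that the trial is underpowered. It is not. The 88% was computed from the total SD, and power without site rises with ρ. At 10%, going from 88.93% to 90.13% keeps 1.20 of the 3.14 points available.

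Local assays are a weak argument for a site effect on creatinine. Section 9.2 does list "Creatinine, BUN, and electrolytes (local laboratory", and section 10.2 does the same for follow-up. But the endpoint is a within-patient change, with baseline in the model, so a constant laboratory offset cancels. Only proportional calibration differences, or real differences in change between sites, would remain.

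Finally, the wording of section 14.2 need not be exhaustive, and a statistical analysis plan that is not at hand may add site. This is a partial defense only: the section fixes the model type, outcomes, covariates and interaction rule, and the one stratification factor is missing from the list.

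**Conclusion.** The mismatch between sections 9.1 and 14.2 is real. Its effect depends on site being related to outcome and runs in the conservative direction: estimates are unbiased and the type I error is not inflated. For an assumed site share of 1 to 10%, the actual alpha is about 2.4 to 1.8% instead of 2.5%, and the forgone power is about 0.2 to 2 points. These figures rest on near-complete balance within site and on the protocol's own effect sizes and SDs. The sample size stands. This is a worthwhile and nearly free improvement to the analysis, not a threat to the trial's validity.

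**What to change.** In section 14.2, add the site factor used for stratification to both primary models. Two forms are suitable: a random intercept for site, or fixed effects with a prespecified rule for pooling small satellites under their regional center. If site is to stay out, the section should say why.

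The text should also state whether the stratum is the regional center or each hospital, since section 9.1 leaves this open. Pooling to the 9 centers may be coarser than the stratum used, and may then recover only part of the precision.

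The listed model has four parameters (intercept, dose, mode, baseline creatinine), leaving 300 − 4 = 296 residual degrees of freedom. Pooling to 9 centers uses 8 of them. Separate fixed effects for every satellite use more: 29 in the 30-site simulation, where simulated power fell by about 0.6 points with no site effect present. Either way the cost is small, and the choice should be fixed before unblinding.

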9.2 Baseline Assessments

At the time of randomization, all study subjects will undergo

- Directed history and physical examination, focused on signs and symptoms of congestion
- Vital signs (including O₂ saturation and weight)
- Concomitant cardiovascular medications
- Creatinine, BUN, and electrolytes (local laboratory)
- Patient Global Well being assessment (PGA) by VAS (see Appendix C)
- Dyspnea assessment by VAS (see Appendix C)
- Blood sample for biomarkers core laboratory

10. FOLLOW UP EVALUATIONS

Follow-up evaluations are expected to occur within +/- 2 hours of the nominal time points.

10.1 6 and 12 hours

- PGA assessment by VAS
- Dyspnea assessment by VAS

10.2 24, 48, 72, and 96 hours

On study days 1-4, all study subjects will undergo the following assessments daily:

- Directed history and physical examination, focused on signs and symptoms of congestion
- Vital signs (including O₂ saturation and weight)
- Creatinine, BUN, and electrolytes (local laboratory)
- PGA assessment by VAS at 24, 48, 72, and 96 hours
- Dyspnea assessment by VAS at 24, 48, 72, and 96 hours
- Fluid balance over preceding 24 hours (net intake net output)
- Blood sample for biomarkers core laboratory (72 hours only)
- Changes in cardiovascular medications
- Assessment for adverse events

10.3 Day 7 or Day of Discharge (if earlier than 7 days)

- Directed history and physical examination, focused on signs and symptoms of congestion
- Vital signs (including O₂ saturation and weight)
- Creatinine, BUN, and electrolytes (local laboratory)
- Blood sample for biomarkers core laboratory
- Changes in cardiovascular medications
- Assessment for adverse events

10.4 Day 60

Patients will return to clinic for Day 60 study-follow up (+/- 7 days). During this clinic visit, they will undergo the following assessments:

- Directed history and physical examination, focused on signs and symptoms of congestion
- Vital signs (including O₂ saturation and weight)
- Changes in cardiovascular medications
- Assessment for adverse events
- Assessment for interval hospitalizations, ED visits, or unscheduled clinic visits
- Creatinine, BUN, and electrolytes (local laboratory)
- Blood sample for biomarkers core laboratory

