4. PRELIMINARY STUDIES

4.1 Safety of Loop Diuretics: Relationship to Mortality

As noted above, the use of loop diuretics is nearly universal in patients with AHF (5). A variety of theoretical considerations suggest potential mechanisms of harm from loop diuretics in heart failure, including activation of the renin-angiotensin-aldosterone system, activation of the sympathetic nervous system, and the induction of vasoconstriction or hypotension. A large body of literature supports the concept of higher mortality in patients receiving higher doses of loop diuretics (6;8;9). In an analysis of the recently completed ESCAPE trial (unpublished data), there was a direct relationship identified between dose of loop diuretics and increased mortality (Figure 1).

and mortality in ESCAPE study.

Confounding this and all other such data is the issue of confounding by indication, i.e., the fact that patients who receive higher doses of diuretics may do so because of greater disease severity compared to patients who can be successfully treated with lower doses of diuretics. Although such confounding can never be completely eliminated, a variety of studies have found a persistent adverse effect of loop diuretics even after multi-variable adjustment for other known predictors of mortality (9;10). In further analyses of data from the ESCAPE trial, total diuretic dose was not clearly linked to other measures of disease severity such as levels of B-type natriuretic peptide (BNP) or to measures of volume overload such as pulmonary capillary wedge pressure (Figure 2). Although such data do not eliminate the problem of confounding by indication, they suggest that dosing of diuretics is not closely linked to other measures of disease severity. Taken as a whole, the available data clearly suggest the presence of a dose related mortality signal with increasing doses of loop diuretic therapy in AHF.

Figure 2. Pulmonary capillary wedge pressure versus maximum in-hospital furosemide dose in ESCAPE.

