Patients will be followed daily during hospitalization for adverse events and for assessing length of stay.

All patients will undergo day 60 follow up visit including physical examination, assessment of interval hospitalizations or ED visits, and assessment of renal function.

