11.2 Secondary Endpoints

- *Weight Loss:* Weight loss will be measured over the 96 hour study period (at 24, 48, 72, and 96 hours from randomization).
- **Proportion of Patients Free of Congestion at 72 hours:** Freedom from congestion will be defined as JVP < 8 cm, no orthopnea, trace peripheral edema or less
- Change in the bivariate relationship of creatinine at 72 hours vs. weight loss at 72 hours: For each of the four treatment groups, weight loss at 72 hours and change in creatinine at 72 hours will be plotted on a two dimensional coordinate grid along with estimates of the mean effect and a 95% confidence ellipse. This will allow visual and statistical assessment of the "trade off" between change in weight and change in renal function. Comparisons among the 6

possible pairwise treatment differences will be constructed to detect differences between treatment strategies.

- Differences in Dyspnea VAS AUC over 24, 48, and 72 hours
- Differences in PGA VAS AUC over 24 and 48 hours
- Change in Serum Creatinine from baseline to 24, 48, 96 hours, day 7/discharge, and 60 days
- Change in Cystatin C from baseline to 72 hours, Day 7/discharge, and 60 days
- Worsening or persistent heart failure: defined as need for rescue therapy (additional open label loop diuretic, addition of thiazide, IV vasoactive agent for heart failure treatment, ultrafiltration, mechanical circulatory or respiratory support) over 72 hours after randomization
- **Development of Cardio-renal syndrome:** defined as increase in serum creatinine > 0.3 mg/dl from randomization at any time point during 72 hours after randomization
- **Treatment Failures**, a composite comprised of ANY ONE of the following during the 72 hours after randomization:
 - o development of cardio-renal syndrome as defined above
 - worsening/persistent heart failure as defined above
 - clinical evidence of over-diuresis requiring intervention (such as administration of IV fluids)
 - o death
- Net fluid loss over study period: Assessed at 24, 48, and 72 hours
- Time from randomization to discharge during index hospitalization
- Total days hospitalized for heart failure or deceased during the 60 days after randomization
- Changes in circulating biomarkers at 72 hours, day 7 (or discharge) and 60 days
- Death or rehospitalization (to include unscheduled clinic visits or ED visits) at 60 days

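### Two secondary outcomes run to day 60, but the only scheduled post-discharge contact that asks about their events may take place from day 53, so up to 7 days can lack planned ascertainment

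*Protocol*

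**What the plan says.** Section 11.2 lists two secondary outcomes with a fixed horizon:

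- "Total days hospitalized for heart failure or deceased during the 60 days after randomization"
- "Death or rehospitalization (to include unscheduled clinic visits or ED visits) at 60 days"

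Section 5 assigns the collection of post-discharge events to one visit: "All patients will undergo day 60 follow up visit including physical examination, assessment of interval hospitalizations or ED visits". Section 10.4 repeats this in its visit list ("Assessment for interval hospitalizations, ED visits, or unscheduled clinic visits") and sets the timing: "Patients will return to clinic for Day 60 study-follow up (+/- 7 days".

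The other follow-up in section 5 ends with the hospital stay: "Patients will be followed daily during hospitalization for adverse events and for assessing length of stay". The schedule in Appendix A has no column between day 7 or discharge and 60 days, and none after 60 days. The protocol describes no telephone contact, record check or vital-status check at day 60.

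**The concern.** The outcome period and the data-collection window do not match. Both outcomes need each patient's status through day 60, but the visit that supplies it may be held a week earlier without any protocol deviation. For a patient seen on day 53, no planned procedure covers days 54 to 60.

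An analysis plan cannot fully repair this. Censoring at last contact is possible in a time-to-event analysis, but section 11.2 describes a count of days and a status at 60 days, and no analysis rule can supply days that nobody asked about.

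At stake are the two secondary outcomes that carry death and rehospitalization beyond the index stay. How completely they are observed would depend partly on when each clinic visit was booked.

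**Working it through.** **Plan's own figure.** The protocol gives no power or sample size for the 60-day outcomes, so there is nothing to reproduce for them. As a check on the reading of the design, the creatinine calculation in section 14.3.1 (150 per group, difference 0.20 mg/dL, SD 0.5 mg/dL, two-sided alpha 0.025) gives 88.9% against the stated 88%. It has no bearing on this point.

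**Inputs**
- Visit window: day 60 ± 7 (section 10.4).
- Outcome period: 60 days from randomization (section 11.2).
- Sample size: 300 (section 5).
- Background risk: 20–30% readmission and 20–30% mortality within six months (section 3), used only to illustrate size.

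**Step 1: the window.** Earliest visit 60 − 7 = day 53; latest 60 + 7 = day 67. The largest gap is 60 − 53 = 7 days, and 7/60 = 11.7% of the period. A visit on day 60 or later leaves no gap.

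**Step 2: average gap.** Assume the visit day V is uniform on [53, 67]. Then E[max(0, 60 − V)] = (7²/2)/14 = 1.75 days, and 1.75/60 = 2.9%. Counted in whole days over the 15 permitted days, it is (7+6+5+4+3+2+1)/15 = 28/15 = 1.87 days, or 3.1%. About half of patients would be affected.

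**Step 3: first events in the gap.** Assume a constant hazard h = −ln(1 − p)/182.5 for six-month risk p, and let F(t) = 1 − exp(−ht). The share of 60-day first events falling after day 53 is [F(60) − F(53)]/F(60). The 60% row is an assumed upper end for a combined outcome (30% + 30%).

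| p | F(53) | F(60) | Share after day 53 | Events per 300, all seen on day 53 | Events per 300, visits even over days 53–67 |
|---|---|---|---|---|---|
| 20% | 6.27% | 7.07% | 11.3% | 2.4 | 0.6 |
| 30% | 9.84% | 11.06% | 11.1% | 3.7 | 1.0 |
| 60% | 23.36% | 26.01% | 10.2% | 7.9 | 2.1 |

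The last column averages 300 × [F(60) − F(min(60, t))] over t = 53, …, 67. If events cluster soon after discharge, the shares are smaller.

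**Step 4: dead days.** A patient known to have died by day 53 is dead through day 60 without any further contact, so only deaths inside the gap can be missed. Take 25% at 182 days, so h = −ln(0.75)/182 = 0.00158 per day.
- Mean dead days by day 60: 60 − [1 − exp(−60h)]/h = 2.76.
- Mean dead days arising in the gap, if every visit were on day 53: exp(−53h) × {7 − [1 − exp(−7h)]/h} = 0.035.
- Ratio: 0.035/2.76 = 1.3%.

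This covers the death component only. Hospital days in the gap could be lost more nearly in proportion to its length.

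**The case against.** The strongest reply is that the visit has a window but event collection has no stated closing date. Death and inpatient hospitalization are serious adverse event criteria (section 13.2.1), adverse events are to be monitored until they stabilize or resolve (section 13.2.2), and death is not on the list of events exempt from the adverse event form. Some late events may therefore reach the site. This stands in part. But the adverse event definition is tied to use of the test article, worsening heart failure is exempt from the form, and nothing guarantees a contact on or after day 60. So the days are not certain to go unobserved; they have no planned ascertainment.

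A symmetric window is also reasonable for the creatinine and biomarker samples taken at the same visit. That stands, and the fix can leave it alone.

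A reader might infer three stronger things that the protocol does not support:

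- *Unobserved days are scored as alive and out of hospital.* No section says so. Incomplete follow-up on secondary outcomes may be handled in an analysis plan that is not shown.
- *The undercount is informative and hides harm in the worse arm.* Nothing suggests that visit timing differs by arm. Non-attendance by sicker patients is a separate problem, which moving the window alone would not cure.
- *The window calls for all-cause death as its own outcome*, given the mortality signal described in section 4.1. That is a question about the endpoint list and does not follow from the visit timing.

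**Conclusion.** The mismatch is real and can be read directly from sections 10.4 and 11.2 and Appendix A: for patients seen before day 60, up to 7 of the 60 days lack planned ascertainment. The 11.7% maximum is plain arithmetic and applies to a patient seen on the first permitted day.

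The expected effect is probably small. The mean gap is 1.75 days (2.9%) if visits are spread evenly. Adding a constant hazard and six-month risks of 20–60%, about 0.6 to 2.1 first events among 300 patients would fall in it. These sizes rest on those assumptions; the protocol gives neither the distribution of visit days nor 60-day event rates.

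The co-primary endpoints, the sample size and their power are unaffected. This is a minor point, worth acting on because it is certain and cheap to close.

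**What to change.** Either of two changes to section 10.4 closes the gap for patients who are reached:

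1. Open the window for event ascertainment at day 60, so that it runs from day 60 to day 67.
2. Keep ± 7 days for the examination and blood samples, and require a brief telephone or record check on or after day 60 for patients seen earlier or not attending. It should cover vital status, hospitalizations, ED visits and unscheduled clinic visits.

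The second is preferable if sites need the flexibility, because it also reaches patients who do not come to clinic. Under either, state that events count only through day 60 for every patient, so that visits on days 61 to 67 do not lengthen the period.

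The cost is slightly less scheduling freedom under the first option, or one short contact per affected patient under the second. Planned unobserved time falls from as much as 7 days to 0 for patients reached, with no change to the sample size or the primary analysis.
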